8.4. Medication Errors

Medication errors may result, in this study, from the administration or consumption of the wrong drug, by the wrong subject, at the wrong time, or at the wrong dosage strength.

Such medication errors occurring to a study participant are to be captured on the medication error CRF which is a specific version of the AE page, and on the SAE form when appropriate. In the event of medication dosing error, the sponsor should be notified immediately.

Medication errors are reportable irrespective of the presence of an associated AE/SAE, including:

- Medication errors involving subject exposure to the investigational product;
- Potential medication errors or uses outside of what is foreseen in the protocol that do or do not involve the participating subject.

Whether or not the medication error is accompanied by an AE, as determined by the investigator, the medication error should be captured on the medication error version of the AE page and, if applicable, any associated AE(s) are captured on an AE CRF page.

8.5. Abnormal Test Findings

The criteria for determining whether an abnormal objective test finding should be reported as an AE are as follows:

- Test result is associated with accompanying symptoms; and/or
- Test result requires additional diagnostic testing or medical/surgical intervention; and/or
- Test result leads to a change in study dosing (outside of protocol-stipulated dose adjustments) or discontinuation from the study, significant additional concomitant drug treatment, or other therapy; and/or
- Test result is considered to be an AE by the investigator or sponsor.

Merely repeating an abnormal test, in the absence of any of the above conditions, does not constitute an AE. Any abnormal test result that is determined to be an error does not require reporting as an AE.

8.6. Serious Adverse Events

An SAE is any untoward medical occurrence at any dose that:

- Results in death;
- Is life-threatening (immediate risk of death);
- Requires inpatient hospitalization or prolongation of existing hospitalization;
- Results in persistent or significant disability/incapacity (substantial disruption of the ability to conduct normal life functions);
- Results in congenital anomaly/birth defect.

Medical and scientific judgment is exercised in determining whether an event is an important medical event. An important medical event may not be immediately life-threatening and/or result in death or hospitalization. However, if it is determined that the event may jeopardize the subject or may require intervention to prevent one of the other AE outcomes, the important medical event should be reported as serious.

Examples of such events are intensive treatment in an emergency room or at home for allergic bronchospasm; blood dyscrasias or convulsions that do not result in hospitalization; or development of drug dependency or drug abuse.

8.6.1. Protocol-Specified Serious Adverse Events

There are no protocol-specified SAEs in this study. All SAEs will be reported by the investigator as described in previous sections, and will be handled as SAEs in the safety database (see section on Serious Adverse Event Reporting Requirements).

8.6.2. Potential Cases of Drug-Induced Liver Injury

Abnormal values in aspartate transaminase (AST) and/or alanine transaminase (ALT) levels concurrent with abnormal elevations in total bilirubin level that meet the criteria outlined below in the absence of other causes of liver injury are considered potential cases of drug-induced liver injury (potential Hy's law cases) and should always be considered important medical events.

The threshold of laboratory abnormalities for a potential case of drug-induced liver injury depends on the subject's individual baseline (baseline of the precedent Study A0221047) values and underlying conditions. Subjects who present with the following laboratory abnormalities should be evaluated further to definitively determine the etiology of the abnormal laboratory values:

- Subjects with AST or ALT and total bilirubin baseline values within the normal range who subsequently present with AST or ALT values ≥ 3 times the upper limit of normal (X ULN) concurrent with a total bilirubin value ≥ 2 X ULN with no evidence of hemolysis and an alkaline phosphatase value ≤ 2 X ULN or not available;
- For subjects with preexisting ALT **OR** AST **OR** total bilirubin values above the ULN, the following threshold values should be used in the definition mentioned above:
 - For subjects with preexisting AST or ALT baseline values above the normal range: AST or ALT values ≥ 2 times the baseline values and ≥ 3 X ULN, or ≥ 8 X ULN (whichever is smaller).

Concurrent with

- For subjects with preexisting values of total bilirubin above the normal range: Total bilirubin level increased from baseline by an amount of at least 1 X ULN **or** if the value reaches ≥ 3 X ULN (whichever is smaller).

The subject should return to the investigational site and be evaluated as soon as possible, preferably within 48 hours from awareness of the abnormal results. This evaluation should include laboratory tests, detailed history, and physical assessment.

In addition to repeating measurements of AST and ALT, laboratory tests should include albumin, creatine kinase, total bilirubin, direct and indirect bilirubin, gamma-glutamyl transferase, prothrombin time (PT)/ international normalized ratio (INR), and alkaline phosphatase. A detailed history, including relevant information, such as review of ethanol, acetaminophen, recreational drug and supplement consumption, family history, occupational exposure, sexual history, travel history, history of contact with a jaundiced person, surgery, blood transfusion, history of liver or allergic disease, and work exposure, should be collected. Further testing for acute hepatitis A, B, or C infection and liver imaging (eg, biliary tract) may be warranted. All cases confirmed on repeat testing as meeting the laboratory criteria defined above, with no other cause for liver function test (LFT) abnormalities identified at the time, should be considered potential Hy's law cases irrespective of availability of all the results of the investigations performed to determine etiology of the abnormal LFTs. Such potential Hy's law cases should be reported as SAEs.

8.7. Hospitalization

Hospitalization is defined as any initial admission (even less than 24 hours) in a hospital or equivalent healthcare facility or any prolongation to an existing admission. Admission also includes transfer within the hospital to an acute/intensive care unit (eg, from the psychiatric wing to a medical floor, medical floor to a coronary care unit, or neurological floor to a tuberculosis unit). An emergency room visit does not necessarily constitute a hospitalization; however, the event leading to the emergency room visit should be assessed for medical importance.

Hospitalization does not include the following:

- Rehabilitation facilities;
- Hospice facilities;
- Respite care (eg, caregiver relief);
- Skilled nursing facilities;
- Nursing homes;
- Same-day surgeries (as outpatient/same-day/ambulatory procedures).

Hospitalization or prolongation of hospitalization in the absence of a precipitating, clinical AE is not in itself an SAE. Examples include:

- Admission for treatment of a preexisting condition not associated with the development of a new AE or with a worsening of the preexisting condition (eg, for workup of persistent pre-treatment laboratory abnormality);

- Social admission (eg, subject has no place to sleep);
- Administrative admission (eg, for yearly physical examination);
- Protocol-specified admission during a study (eg, for a procedure required by the study protocol);
- Optional admission not associated with a precipitating clinical AE (eg, for elective cosmetic surgery);
- Hospitalization for observation without a medical AE;
- Preplanned treatments or surgical procedures. These should be noted in the baseline documentation for the entire protocol and/or for the individual subject;

Diagnostic and therapeutic noninvasive and invasive procedures, such as surgery, should not be reported as AEs. However, the medical condition for which the procedure was performed should be reported if it meets the definition of an AE. For example, an acute appendicitis that begins during the AE reporting period should be reported as the AE, and the resulting appendectomy should be recorded as treatment of the AE.

8.8. Severity Assessment

If required on the AE CRFs, the investigator will use the adjectives MILD, MODERATE, or SEVERE to describe the maximum intensity of the AE. For purposes of consistency, these intensity grades are defined as follows:

MILD	Does not interfere with subject's usual function.
MODERATE	Interferes to some extent with subject's usual function.
SEVERE	Interferes significantly with subject's usual function.

Note the distinction between the severity and the seriousness of an AE. A severe event is not necessarily an SAE. For example, a headache may be severe (interferes significantly with the subject's usual function) but would not be classified as serious unless it met one of the criteria for SAEs, listed above.

8.9. Causality Assessment

The investigator's assessment of causality must be provided for all AEs (serious and nonserious); the investigator must record the causal relationship in the CRF, as appropriate, and report such an assessment in accordance with the SAE reporting requirements if applicable. An investigator's causality assessment is the determination of whether there exists a reasonable possibility that the investigational product caused or contributed to an AE; generally the facts (evidence) or arguments to suggest a causal relationship should be provided. If the investigator does not know whether or not the investigational product caused the event, then the event will be handled as "related to investigational product" for reporting purposes, as defined by the sponsor (see section on Reporting Requirements). If the investigator's causality assessment is "unknown but not related to investigational product," this should be clearly documented on study records.

In addition, if the investigator determines that an SAE is associated with study procedures, the investigator must record this causal relationship in the source documents and CRF, as appropriate, and report such an assessment in accordance with the SAE reporting requirements, if applicable.

8.10. Exposure During Pregnancy

For investigational products and for marketed products, an exposure during pregnancy occurs if:

1. A female becomes, or is found to be, pregnant either while receiving or having been exposed (eg, because of treatment or environmental exposure) to the investigational product; or the female becomes, or is found to be pregnant after discontinuing and/or being exposed to the investigational product;

An example of environmental exposure would be a case involving direct contact with a Pfizer product in a pregnant woman (eg, a nurse reports that she is pregnant and has been exposed to chemotherapeutic products).

2. A male subject has been exposed (eg, because of treatment or environmental exposure) to the investigational product prior to or around the time of conception and/or is exposed during his partner's pregnancy.

If a study subject or study subject's partner becomes or is found to be pregnant during the study subject's treatment with the investigational product, the investigator must submit this information to the Pfizer drug safety unit on a Serious Adverse Event (SAE) Report Form and Exposure During Pregnancy (EDP) supplemental form, regardless of whether an SAE has occurred. In addition, the investigator must submit information regarding environmental exposure to a Pfizer product in a pregnant woman (eg, a subject reports that she is pregnant and has been exposed to a cytotoxic product by inhalation or spillage) using the EDP supplemental form. This must be done irrespective of whether an AE has occurred and within 24 hours of awareness of the exposure. The information submitted should include the anticipated date of delivery (see below for information related to termination of pregnancy).

Follow-up is conducted to obtain general information on the pregnancy and its outcome for all EDP reports with an unknown outcome. The investigator will follow the pregnancy until completion or until pregnancy termination) and notify Pfizer of the outcome as a follow-up to the initial EDP supplemental form. In the case of a live birth, the structural integrity of the neonate can be assessed at the time of birth. In the event of a termination, the reason(s) for termination should be specified and, if clinically possible, the structural integrity of the terminated fetus should be assessed by gross visual inspection (unless preprocedure test findings are conclusive for a congenital anomaly and the findings are reported).

If the outcome of the pregnancy meets the criteria for an SAE (ie, ectopic pregnancy, spontaneous abortion, intrauterine fetal demise, neonatal death, or congenital anomaly [in a live born, a terminated fetus, an intrauterine fetal demise, or a neonatal death]), the investigator should follow the procedures for reporting SAEs.

Additional information about pregnancy outcomes that are reported as SAEs follows:

- Spontaneous abortion includes miscarriage and missed abortion;
- Neonatal deaths that occur within 1 month of birth should be reported, without regard to causality, as SAEs. In addition, infant deaths after 1 month should be reported as SAEs when the investigator assesses the infant death as related or possibly related to exposure to investigational product.

Additional information regarding the exposure during pregnancy may be requested by the investigator. Further follow-up of birth outcomes will be handled on a case-by-case basis (eg, follow-up on preterm infants to identify developmental delays). In the case of paternal exposure, the investigator will provide the study subject with the Pregnant Partner Release of Information Form to deliver to his partner. The investigator must document in the source documents that the subject was given the Pregnant Partner Release of Information Form to provide to his partner.

8.11. Occupational Exposure

An occupational exposure occurs when during the performance of job duties, a person (whether a healthcare professional or otherwise) gets in unplanned direct contact with the product, which may or may not lead to the occurrence of an AE.

An occupational exposure is reported to safety within 24 hours of Investigator's awareness, using the SAE Report form, regardless of whether there is an associated AE/SAE. Since the information does not pertain to a subject enrolled in the study, the information is not reported on a CRF, however a copy of the completed SAE Report form is maintained in the study master file.

8.12. Withdrawal Due to Adverse Events (See Also Section on Subject Withdrawal)

Withdrawal due to AE should be distinguished from withdrawal due to other causes, according to the definition of AE noted earlier, and recorded on the appropriate AE CRF page.

When a subject withdraws because of an SAE, the SAE must be reported in accordance with the reporting requirements defined below.

8.13. Eliciting Adverse Event Information

The investigator is to report all directly observed AEs and all AEs spontaneously reported by the study subject/parent/legally acceptable representative. In addition, each study subject/parent/legally acceptable representative will be questioned about AEs.

8.14. Reporting Requirements

Each AE is to be assessed to determine if it meets the criteria for SAEs. If an SAE occurs, expedited reporting will follow local and international regulations, as appropriate.

8.14.1. Serious Adverse Event Reporting Requirements

If an SAE occurs, Pfizer is to be notified within 24 hours of investigator awareness of the event.

In particular, if the SAE is fatal or life-threatening, notification to Pfizer must be made immediately, irrespective of the extent of available AE information. This time frame also applies to additional new information (follow-up) on previously forwarded SAE reports as well as to the initial and follow-up reporting of exposure during pregnancy, exposure via breastfeeding and occupational exposure cases.

In the rare event that the investigator does not become aware of the occurrence of an SAE immediately (eg, if an outpatient study subject initially seeks treatment elsewhere), the investigator is to report the event within 24 hours after learning of it and document the time of his or her first awareness of the AE.

For all SAEs, the investigator is obligated to pursue and provide information to Pfizer in accordance with the time frames for reporting specified above. In addition, an investigator may be requested by Pfizer to obtain specific additional follow-up information in an expedited fashion. This information collected for SAEs is more detailed than that captured on the AE CRF. In general, this will include a description of the AE in sufficient detail to allow for a complete medical assessment of the case and independent determination of possible causality. Information on other possible causes of the event, such as concomitant medications, vaccines, and/or illnesses, must be provided. In the case of a subject death, a summary of available autopsy findings must be submitted as soon as possible to Pfizer or its designated representative.

8.14.2. Nonserious Adverse Event Reporting Requirements

All AEs will be reported on the AE page(s) of the CRF. It should be noted that the form for collection of SAE information is not the same as the AE CRF. Where the same data are collected, the forms must be completed in a consistent manner. For example, the same AE term should be used on both forms. AEs should be reported using concise medical terminology on the CRFs as well as on the form for collection of SAE information.

8.14.3. Sponsor Reporting Requirements to Regulatory Authorities

AE reporting, including suspected unexpected serious adverse reactions, will be carried out in accordance with applicable local regulations.

9. DATA ANALYSIS/STATISTICAL METHODS

Detailed methodology for summary and statistical analyses of the data collected in this trial will be documented in a [Statistical Analysis Plan](#), which will be dated and maintained by the Sponsor. This document may modify the plans outlined in the protocol; however, any major modifications of the primary endpoint definition and/or its analysis will also be reflected in a protocol amendment.

9.1. Sample Size Determination

No target number of subjects is determined.

This is an extension study for the subjects who completed Study A0221047 in Japan and the primary objective is to investigate the safety and tolerability of fesoterodine for these subjects. No statistical testing will be planned but descriptive statistics will be used along

with subject narratives. Therefore, the number of subjects to be enrolled in this study is not based on any formal sample size calculation.

In Study A0221047, a few Japanese subjects in cohort 1 (body weight >25 kg) and 9 Japanese subjects in cohort 2 (body weight ≤25 kg) are planned to be enrolled as potential candidate subjects for this study. Assuming a 12.5% drop-out rate in Study A0221047, out of Japanese subjects who are enrolled to Study A0221047, approximately 9 subjects are expected to be enrolled in this study.

9.2. Efficacy Analysis

9.2.1. Efficacy Analysis Sets

All efficacy analysis will be used the following full analysis set.

9.2.1.1. Full Analysis Set (FAS)

The Full Analysis Set will include all subjects who have been enrolled and received at least one dose of study medication and have at least 1 observation in efficacy endpoint data after baseline visit in this study.

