Assess Study Medication compliance	X ^a		X			X	

a. The Week 0 visit of Study A0221109 is the same visit as Week 24 visit of Study A0221047. All procedures done at Week 24 visit of Study A0221047 will be used as the Week 0 data for Study A0221109. These procedures (Study A0221047 procedures) will not be repeated at Week 0 of Study A0221109.

b. Or in the event of the subject withdrawing early from the study. Urodynamic assessment should only be performed in subjects who have not missed any doses in the 3 days prior to the visit.

c. Telephone calls may be substituted by a clinic visit at the discretion of the investigator.

d. If vital signs or physical examinations show a clinically relevant change from baseline of the precedent Study A0221047, then safety monitoring will occur at a minimum of monthly intervals, or more frequently as clinically appropriate, until the abnormality resolves.

e. PVR only in subjects who are not performing intermittent catheterization or in any subjects who have >1 urinary tract infection (UTI) during the study.

f. Laboratory assessments may be repeated as needed to follow-up on significant findings.

g. Urinalysis: Urine microscopy, culture, and sensitivity to be performed in the event of the presence of symptoms (eg, fever, flank pain), positive leucocytes and/or nitrites on urinalysis, or if the subject has a documented history of vesicoureteral reflux (VUR).

h. Only for female subjects of child-bearing potential. Pregnancy tests may also be repeated as per request of Institutional Review Board (IRB)/Ethics Committee (EC) or if required by local regulations.

i. The bladder diary will be completed for 3 days prior to Final Visit.

j. The dosing log will be completed on a daily basis.

k. At Final Visit, the time of last dose should be recorded.

l. Follow up visit will be done at 4 weeks after Final Visit.

Table 2. Subjects who were randomized to Oxybutynin arm in Study A0221047

Visit	Visit 1	Visit 2	Visit 3	Visit 4	Visit 5	Visit 6	Visit 7	Final Visit ^b	Follow-Up Visit ^l
Week (Weeks from baseline of the precedent Study A0221047)	Week 0 (24)	Week 6 (30)	Week 12 (36)	Week 18 (42)	Week 24 (48)	Week 28 (52)	Week 34 (58)	Week 40 (64)	Week 44 (68)
Allowance (weeks)	-	±2	±2	±2	±2	±2	±2	±2	+2
Clinic visit/Phone call	Clinic visit	Phone call ^c	Clinic visit	Phone call ^c	Phone call ^c	Clinic visit	Phone call ^c	Clinic visit	Phone call ^c
Informed Consent & Assent	X								
Demography	X								

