6.3. Additional Contacts

Other contacts may also be made, as appropriate, to provide reminders to the subject to complete the bladder diary and daily dosing log. Contacts may take the form of telephone calls. Subjects should be contacted:

- Approximately 1 week prior to Final visit, to remind the subject to complete the bladder diary and to review instructions on proper completion if needed.

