6.4. Subject Withdrawal

If treatment is inadequate or the subject cannot tolerate the dose of fesoterodine, consideration should be given to withdrawal.

Subjects may withdraw from the study at any time at their own, or their legal representative(s) request, or they may be withdrawn at any time at the discretion of the investigator or sponsor for safety or behavioral reasons, or the inability of the subject to comply with the protocol required schedule of study visits or procedures at a given study site.

If a subject does not return for a scheduled visit, every effort should be made to contact the subject. All attempts to contact the subject and information received during contact attempts must be documented in the subject's medical record. In any circumstance, every effort should be made to document subject outcome, if possible. The investigator should inquire about the reason for withdrawal, request the subject to return all unused investigational product(s), request the subject to return for a final visit, if applicable, and follow-up with the subject regarding any unresolved AEs.

If a subject withdraws from the study prior to Final visit (Week 28 in subjects who were randomized to Fesoterodine arms in Study A0221047, or Week 40 in subjects who were randomized to Oxybutinin arm in Study A0221047), the same assessments as at Final

visit should be performed if possible. Urodynamic assessment should only be performed in subjects who have not missed any doses in the 3 days prior to the visit.

Subjects who withdraw early from the study and who have taken at least 1 dose of study medication should also be contacted by telephone approximately 4 weeks after stopping study medication, and have the same assessments performed as at Follow-up visit.

If the subject withdraws from the study, and they or their legal representative(s) also withdraw consent for disclosure of future information, no further evaluations should be performed, and no additional data should be collected. The sponsor may retain and continue to use any data collected before such withdrawal of consent.

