7.1. Efficacy Assessments

7.1.1. Urodynamic Assessments

Urodynamic assessment will be performed by persons qualified to perform pediatric urodynamics by education, training and experience, in accordance with International Children's Continence Society standards at Final Visit (Neveus, et al, 2006).⁵ It should be performed with the subject awake, or if necessary under sedation, but general anesthesia is not permitted under this protocol. Typically a multichannel technique through a dual-lumen urodynamic catheter should be used. The bladder will be filled at a constant fill rate with test medium warmed to body temperature, until maximum cystometric capacity is reached as defined below, or in the judgement of the investigator, filling should be stopped.

Expected bladder capacity (EBC) for age (mL) = $[30 + (\text{child's age in years} \times 30)]$ mL up to the age of 12 years. From the age of 12 years onwards EBC is relatively constant at 390 mL.

The infusion rate should be based on 5% of expected bladder capacity per minute and will be recorded on the case report form (CRF).

The following will be evaluated:

- Maximum cystometric capacity, defined as maximal tolerable cystometric capacity, until voiding or leaking begins, or at a pressure of ≥ 40 cm H₂O.
- Detrusor pressure at maximum bladder capacity.

- Maximum detrusor pressure.
- Presence of IDC.
- Bladder volume at first IDC, if present.
- Bladder wall compliance (mL/cm H₂O), defined as $\Delta\text{volume}/\Delta\text{pressure}$ during that change in bladder volume.
- Presence of subtraction test (eg, cough) on urodynamic trace.

Where possible, urodynamic assessments for a subject should be performed by the same person in both this study and Study A0221047. Only the central reader's assessment of the urodynamic evaluation should be recorded in the CRF.

Prophylactic antimicrobial treatment may be administered at the discretion of the investigator and in line with local practice.

Attempts should be made to perform an urodynamic assessment in subjects who withdraw prior to Final Visit and who have not missed any doses in the 3 days prior to the visit.

Full technical details are provided separately.

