5. ANALYSIS SETS

5.1. Full Analysis Set

The Full Analysis Set will include all subjects who have been enrolled and received at least one dose of study medication and have at least 1 observation in efficacy endpoint data after baseline visit in Study A0221109.

The Full Analysis Set (FAS) will be used for all efficacy analyses.

For all efficacy analyses, the data from Study A0221047 and Study A0221109 will be merged (see the details in [Section 8.1](#)).

5.2. ‘Per Protocol’ Analysis Set

Not applicable.

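### The FAS needs an efficacy observation after Week 0, but each child has only one planned occasion for it, so a dosed child who leaves unassessed also drops out of the A0221047 baseline and Week 12 summaries

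*Protocol*

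**What the plan says.** **Who is in the set.** Protocol 9.2.1.1 requires enrolment, at least one dose, and that the child "have at least 1 observation in efficacy endpoint data after baseline visit in this study". SAP 5.1 has the same condition: "have at least 1 observation in efficacy endpoint data after baseline visit in Study A0221109". It adds: "The Full Analysis Set (FAS) will be used for all efficacy analyses". The Safety Analysis Set in SAP 5.3 requires only enrolment and one dose.

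**When efficacy is measured.** In Tables 1 and 2 of the Schedule of Activities, urodynamics and the diary are marked only in the Final Visit column (Week 28, or Week 40 for former oxybutynin subjects). Protocol 7.1.1 places urodynamics under "Continence Society standards at Final Visit", and footnote i of both tables says: "The bladder diary will be completed for 3 days prior to Final Visit". The Week 12 clinic visit of this study has no efficacy assessment.

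**Early withdrawal.** Footnote b extends the Final Visit column to children who withdraw early, and Protocol 6.1.5, 6.2.7 and 6.4 ask for the same assessments then. Section 6.4 makes this conditional on feasibility, and for urodynamics it adds: "Urodynamic assessment should only be performed in subjects who have not missed any doses in the 3 days prior to the visit".

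**What is summarised.** Protocol 9.2.2 and SAP 8.2.1 summarise efficacy on merged data from A0221047 baseline onward. SAP Table 3 lists Week 12 (which is Week 12 of A0221047, per SAP Table 4), Week 52 or Week 64, and Final Visit. SAP 7 plans no imputation.

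**The concern.** A condition of at least one post-baseline observation usually does little harm, because most trials offer several chances to meet it. Here there is one, at the end of treatment or on leaving. Whether a child counts at A0221047 baseline and Week 12 therefore depends on whether an assessment was obtained months later.

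That dependence may be related to outcome. Protocol 6.4 states: "If treatment is inadequate or the subject cannot tolerate the dose of fesoterodine, consideration should be given to withdrawal". A child who stops for either reason may have missed doses in the last 3 days, which rules out urodynamics. The child may also have no diary, since it has to be filled in before the visit. The one reminder the protocol describes is timed "Approximately 1 week prior to Final visit, to remind the subject to complete the bladder diary", and nothing says how a child who stops unexpectedly is to have a diary ready.

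At stake is the secondary objective, long-term efficacy. The baseline and Week 12 rows could describe a group partly selected on later success, and the IDC percentages would leave out the unassessed children without saying so.

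**Working it through.** **1. The plan's own figure.** Protocol 9.1 expects about 9 children, from 9 Japanese subjects in cohort 2 plus 'a few' in cohort 1, with 12.5% drop-out in A0221047. Expected entrants = (9 + few) × (1 − 0.125). For few = 1, 2, 3 this gives 8.75, 9.6 and 10.5, which agrees with about 9.

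**2. What happens to each kind of child under the current rule.**

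| Child, dosed in A0221109 | In FAS? | A0221047 baseline and Week 12 rows | Week 52/64 or Final Visit rows |
|---|---|---|---|
| Completes, assessed | Yes | Counted | Counted |
| Withdraws, diary or urodynamics obtained | Yes | Counted | Counted in the Final Visit row for what was measured (SAP Table 4: last assessment after Day 169) |
| Leaves with neither | No | Removed | Nothing to count |

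The baseline and Week 12 data of the third child should exist, because inclusion criterion 1 requires completion of A0221047 with all its visit procedures.

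**3. Withdrawals, under a stated assumption.** The documents give no rate for the extension. Assume that 12.5% per 24 weeks continues at a constant rate:
- Rate: ln(0.875) = −0.1335 per 24 weeks.
- By Week 28: 1 − exp(−0.1335 × 28/24) = 14.4%.
- By Week 40: 1 − exp(−0.1335 × 40/24) = 20.0%.

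Only former oxybutynin children go to Week 40, and that arm is in cohort 1, which supplies only a few children:
- None of 9 from oxybutynin: 9 × 0.144 = 1.3.
- One: 8 × 0.144 + 1 × 0.200 = 1.35.
- Three: 6 × 0.144 + 3 × 0.200 = 1.46.

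So about 1.3 to 1.5 withdrawals. If half of them were assessed, about 0.65 to 0.75 child would be excluded; if all were, none.

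**4. Range for exclusion itself.** Let r be the assumed chance that a child leaves with no efficacy assessment, with n = 9. Expected excluded = 9r; chance of at least one = 1 − (1 − r)^9.

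| r | Expected excluded | Chance of at least one |
|---|---|---|
| 5% | 0.45 | 37% |
| 6.25% (12.5% withdraw, half assessed) | 0.56 | 44% |
| 12.5% (12.5% withdraw, none assessed) | 1.1 | 70% |
| 20% | 1.8 | 87% |
| 30% | 2.7 | 96% |

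**5. Effect on the rows.** Each excluded child is 1/9 = 11% of the sample. If one child with Week 12 change x is excluded and the other eight average m, the FAS row shows m and the row for all dosed children is (8m + x)/9 = m − (m − x)/9. The row moves by one ninth of the gap between that child and the rest.

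For IDC, suppose one child is excluded and 4 of the other 8 have no contractions (invented counts). The table shows 4/8 = 50%. With all dosed children as denominator it is 4/9 = 44%, with 1/9 = 11% not assessed.

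For continuous endpoints at Week 52/64 and Final Visit, the excluded child has no value and none is imputed, so the means are the same under either definition.

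**The case against.** A reader might infer that the FAS is simply a completers' set. The documents do not support that. Assessment at early withdrawal is planned, one observation on any efficacy endpoint is enough, the 3-day dosing condition restricts urodynamics only, and SAP Table 4 counts a withdrawal assessment in the Final Visit row. Nor is it right that withdrawers have no planned diary: diary review is part of the early-withdrawal visit, and Protocol 7.1.2 accepts 2 days. What can be said is that a diary is not assured.

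The losses are also not wholly hidden. N is reported for continuous summaries, FAS size can be compared with the Safety Analysis Set, and Protocol 9.2.2 promises a narrative of efficacy and safety for each subject, not stated to be limited to the FAS. That stands. However, SAP 8.2.1 does not mention the narratives among the efficacy outputs, and neither N nor a narrative puts the child back into the summary rows.

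The strongest argument is that a new FAS cannot repair the late means and that keeping the same children in every row is defensible. The first half is correct. The second is weaker than it looks, because the current rule does not achieve it: a withdrawer with a diary but no urodynamics is in the FAS, counts in the baseline urodynamic row and is absent from the late one.

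Finally, the study is descriptive, has no hypotheses, and its primary objective is safety. That limits the weight of the point.

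**Conclusion.** The point holds in a limited form. The FAS is completers plus assessed early withdrawers. A dosed child who leaves unassessed is removed from the A0221047 baseline and Week 12 efficacy summaries as well, for reasons that may be related to inadequate effect or intolerance. On the assumption that the A0221047 drop-out rate carries over, 1.3 to 1.5 of 9 children would withdraw and at most that many would be excluded, each being 11% of the sample. The extension's true rate could be lower, since entrants have already completed 24 weeks and tolerated treatment.

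A reader might apply the 20% Week 40 figure to all 9 children and expect 1.8 withdrawals. The design does not support this, because only the few former oxybutynin children are treated that long. A reader might also infer that the late continuous means would change under a different FAS; with no imputation they would not. The safety analysis is unaffected. This is a cheap improvement to a secondary, descriptive objective.

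**What to change.** - In Protocol 9.2.1.1 and SAP 5.1, define the FAS as all subjects enrolled and given at least one dose in A0221109, as for the Safety Analysis Set in SAP 5.3, and drop the post-baseline observation condition.
- Keep observed data at each visit, with no imputation.
- At Week 52/64 and Final Visit, add a row with the number of FAS subjects not assessed and the reason for withdrawal.
- In the IDC table, show 'not assessed' as a category so that percentages refer to all FAS subjects.

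**Cost.** One sentence in each document, one table row and one category, with no new data. The small downside is that N will differ between visit rows, so change from baseline at each visit should be read in the children observed at that visit. The change cannot recover late values that were never measured; it restores the earlier rows and makes the late gaps visible.
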